7.2.2 Standard of care Study Procedures

At Visit 1 (Screening/Baseline), in addition to study specific examinations, the Investigator will perform pre-operative examinations that are part of the Investigator's standard pre-operative evaluations for a potential subject being considered for cataract surgery.

At the operative visit (Visit 3) for each study subject, the Surgeon/Investigator will use their standard surgical procedure for the extraction of the cataract. The procedure for the implantation of an IOL will be based upon the package insert of the intraocular lens being implanted. The procedures use for the extraction of the cataract and implantation of an IOL should be consistent for all study related cases.

Pre-, intra- and post-operative open-label medications will be used as is customary for the Surgeon/Investigator and should be consistent for all cases. However the use of any pre-, intra- or post-operative NSAID or corticosteroid is prohibited.

At the conclusion of the study, a study subject may be scheduled for additional, non-study related, post-operative examinations based upon the Surgeon/Investigator's standard of care.

7.3 Laboratory Procedures/Evaluations

N/A.

7.4 Study Visit Schedule

7.4.1 Visit 1: (Screening/Baseline Visit, Day -30 to -1)

A potential study subject qualifications will be assessed according to the inclusion/exclusion criteria listed in the protocol (see [Sections 5.1, 5.2 and 5.3](#)). Prior to undergoing any study-specific procedures, both the study Informed Consent and Authorization for Use/Disclosure of Health Information forms (HIPAA authorization) must be signed by a potential subject who has agreed to participate in the study. During this visit, the following information will be collected/evaluated and recorded in the appropriate sections of the study case report forms for both eyes:

- a. Obtain informed consent and HIPAA release
- b. Record the subject's demographic data and prior 12 month medical history
- c. Record the use of all systemic, topical and/or ophthalmic concomitant medications over the previous 30 days
- d. Urine pregnancy test (if applicable)
- e. Investigator evaluation of ocular pain
- f. Monocular Distance Visual Acuity, Uncorrected and Best-Corrected
- g. Manifest Refraction
- h. Slit-lamp examination
- i. Evaluation of lower punctum (scheduled study eye only)
- j. Type and grade of cataract (scheduled study eye only)
- k. Fundus examination (scheduled study eye only)

A subject who meets all of the study inclusion/exclusion criteria will be scheduled for surgery. Each qualified subject will be scheduled to return to the Investigators office 1 to 2 days before their scheduled surgery for the insertion of the study punctal plug.

7.4.2 Visit 2: (Masked Punctal Plug Insertion Visit, 1-2 days pre-op)

Each qualified study subject as they are enrolled in to the study will be sequentially assigned an ID number. Treatment assignments for this study have been randomized (see [Section 10.6.1](#) for details on treatment randomization) to determine which one of the two treatments the study subject will receive during the study. In addition, the ID number and the study subject initials will be recorded on study case report forms, in lieu of recording their name, in order to maintain subject confidentiality.

At this visit the following will be performed and recorded:

- a. Investigator evaluation of ocular pain
- b. Insertion of the assigned masked punctal plug in to the lower punctum of the schedule surgical eye
- c. Inspection of the masked punctal plug via the slit lamp to ensure the plug is properly positioned, with the cap still visible and secured in place.

NOTE: The position of the masked punctal plug may be adjusted with forceps

- d. Recording of any reported adverse event(s).
- e. Concomitant medication

7.4.3 Visit 3: (Surgical Visit, Day 0)

Cataract surgery (e.g., corneal incision, anterior capsulotomy, fragmentation/removal of the lens/cataract) may be performed with the assistance of a femtosecond laser. It is recommended the surgeon use a standard phacoemulsification extraction surgical technique. The anterior capsulotomy should be a well centered continuous curvilinear capsulorhexis approximately 5.5 mm in diameter and the lens must be placed in the capsular bag. A viscoelastic should be used to protect the endothelium. At this visit the following surgical data will be recorded:

- a. Surgical Eye Pupil measurements (prior to and immediately following surgery)
- b. Monocular cataract extraction/IOL implantation recording the following information:
 - Indicate the incision Type (clear cornea, limbal, sclera), Location (nasal, temporal, superior, other) and Size (mm)
 - Nucleus removal time (< 1min, 1 - < 2 min, 2 - < 3 min, 3 - < 4 min, >4 min)
 - Ease of Cortex removal (Very Easy, Easy, Difficult, Very Difficult)
 - Effective Phaco Power (recording of phaco time and power)
 - Type of IOL (e.g., monofocal, toric, etc.) and lens power
 - Record any surgical complications
- c. Visual Inspection of the masked punctal plug at the conclusion of surgery
- d. Subject reported AEs prior to or after surgery
- e. Concomitant medication

Should a surgical complication occur, implantation of the lens will be at the Investigator's discretion. If any of the surgical complications occur, as listed in [Section 5.3](#), the study subject's punctal plug will be removed after surgery and the subject terminated from the study.

Pre-, intra- and post-operative open-label medications will be used as is customary for the Surgeon/Investigator, and should be consistent for all cases. All pre-, intra- and post-operative open-label medications must be recorded on the Concomitant Medication CRF. However the use of any pre-, intra- or post-operative NSAID or corticosteroid is prohibited, with the exception of a subject who has been prescribed and has been taking a baby aspirin (≤ 81 mg/daily). An LRI or AI procedure required for any sphere/cylinder correction before, during or after cataract surgery is prohibited during the study period.

Each study subject will be scheduled to return within 1, 3, 7 and 14 days after their surgical procedure. The Surgeon/Investigator and/or his/her staff will review with each study subject the proper use or discontinuation of any post-op open-label medications prescribed by the Investigator.

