6.1.7.2 Punctal Plug extruded pre-operative

If a study subject extrudes their plug prior to surgery, a new plug will be inserted in the lower punctum of the subject's scheduled surgical eye. The study subject will then be rescheduled for surgery in 1 to 2 days after re-insertion of the new plug. The punctal plug will remain in the study subject's lower punctum during cataract surgery and for a period of 2 weeks following surgery.

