6.1.7.3 Punctal Plug extruded during surgery

If a study subject extrudes their plug during the surgical procedure, a new plug will be inserted in to the lower punctum of the subject's surgical eye upon completion of the surgery. The punctal plug will remain in the study subject's lower punctum for a period of 2 weeks following surgery.

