6.1.7.4 Punctal Plug extruded after surgery

A study subject that has noticed a plug has been extruded or lost during the follow-up period after surgery should immediately contact the Investigator and/or his/her staff and return to the Investigator's office as soon as possible. The Investigator will discontinue the study subject from the study and place them on open-label post-op medication(s) deemed necessary for the patient's welfare by the Investigator.

For any study subject where the plug has been lost, the Investigator will retro-illuminate or palpate the canaliculi to confirm the plug has not migrated into the canal. Information regarding the loss of any plug must be recorded in the source documents, CRFs and Accountability Logs.

NOTE: If an extruded plug can be located by a study subject, the plug should be returned and collected by the Investigator and/or his/her staff. If the plug tears or has separated, report this as a technical complaint ([Section 8.6](#)). Retain the plug for accountability of investigational supplies.

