7.4.7 Unscheduled Visit

The Investigator has the option of bringing a study subject back in for an unscheduled visit during the treatment period for safety reasons [e.g., study subject complaint of moderate to severe ocular symptom(s), an AE]. An unscheduled visit CRF should be completed. At minimum, the Investigator should record the following:

- a. Investigator evaluation of ocular pain

NOTE: The Investigator that interviewed and record the subject's response to ocular pain at Visit 4 (Day 1 post-op) should interview the subject at this visit

- b. Inspection of the masked punctal plug via the slit lamp, if applicable
- c. Monocular Distance Visual Acuity (Uncorrected)
- d. Slit-Lamp examination

NOTE: The Investigator that slit-lamp evaluation at Visit 4 (Day 1 post-op) should perform the slit-lamp evaluation at this visit.

- e. Recording of any reported adverse event(s).
- f. Concomitant medication

Any changes, discontinuation or addition of an open-label medication(s) must be recorded on the Concomitant Medication CRF.

Table 1: Schedule of Assessments, Events

EXAM PARAMETERS	v1	v2	v3	v4	v5	v6	v7
Inform Consent/HIPPA	①						
Demographic data/Medical Hx/Medication Use	① A						
Concomitant Medication	①	②	③	④	⑤	⑥	⑦
Urine Pregnancy Test (if applicable)	① B						
Subject Randomization to Treatment		②					
Investigator Evaluation of Ocular Pain	① C	②		④ F	⑤ F	⑥ F	⑦ F
Uncorrected Distance VA	① C				⑤	⑥	⑦
Manifest Refraction	① C					⑥	⑦
Best-Corrected Distance VA	① C					⑥	⑦
Slit Lamp Examination	① C			④ F	⑤ F	⑥ F	⑦ F
Insertion of Masked Punctal Plug		②					
Inspection of Masked Punctal Plug		② D	③ E	④ D	⑤ D	⑥ D	⑦ D
Evaluation of lower puncta	①						
Pupil Measurements			③ G				
Type and Grade Cataract	①						
Monocular Cataract Extraction/IOL Implantation			③				
Fundus Examination	①						⑦
Removal of Masked Punctal Plug							⑦ H
Adverse Event Recording		②	③	④	⑤	⑥	⑦

Keys to Abbreviations:

- A = Prior 12 months
- B = Pregnancy test (women of childbearing potential)
- C = Evaluation of Both Eyes
- D = Evaluation using slit-lamp
- E = Visual inspection after surgery
- F = Investigator that performs the slit-lamp and/or ocular pain evaluation at Visit 4 (Day 1 post-op) should perform ALL post-op visit evaluations
- G = Measurement to occur prior to surgery and immediately after surgery
- H = All masked punctal plugs must be removed at the subject last visit

Visit Schedule:

- v1 = Day -30 to -1
- v2 = 1 to 2 days prior to surgery
- v3 = Surgery Day

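### No plug inspection is scheduled between insertion and the end of surgery, so an unnoticed pre-operative loss would bypass Section 6.1.7.2 and could not be told apart from an intra-operative one

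*Combined protocol and SAP*

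**What the plan says.** Section 7.4.2 (Visit 2, 1 to 2 days before surgery) requires a slit-lamp check, once the plug is in, that it is correctly seated. The next scheduled inspection is item c of Section 7.4.3 (Visit 3, surgery): "Visual Inspection of the masked punctal plug at the conclusion of surgery". Table 1 and the synopsis schedule agree. Visit 3 carries key E, "E = Visual inspection after surgery", while Visit 2 and Visits 4 to 7 carry key D (slit lamp).

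The rule for a lost plug depends on when it was lost:

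- **Before surgery (6.1.7.2):** a new plug is inserted and surgery is moved. "The study subject will then be rescheduled for surgery in 1 to 2 days after re-insertion of the new plug".
- **During surgery (6.1.7.3):** the plug is replaced once surgery is finished, with no rescheduling. "If a study subject extrudes their plug during the surgical procedure, a new plug will be inserted in to the lower punctum".
- **After surgery (6.1.7.4):** the subject is discontinued.

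Section 6.1.8 intends the plug to be worn from 1 to 2 days before surgery, through the operation, and for two weeks after it. Section 6.2 asks for the suspected date of any loss in the accountability log and CRF. Section 11.1 (item g) asks for the dates of loss and re-insertion in the source documents.

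**The concern.** Section 6.1.7.2 can be applied only if someone knows, before the operation, that the plug has gone. No scheduled step establishes this. A plug that came out unnoticed the evening before would first be found missing at the end of surgery, where it looks the same as an extrusion during the operation.

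Three things are at stake:

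- **Exposure.** An active-arm eye could go through surgery without the plug that Section 6.1.8 intends to be there. Any effect on efficacy would be expected mainly at Day 1, the first of the four primary time points.
- **Classification.** Pre-operative and intra-operative losses would be mixed in the record, so plug retention, a basic feature of a new delivery device, would be misdescribed.
- **Dating.** The date that Sections 6.2 and 11.1 ask for could not be fixed for such a loss.

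**Working it through.** **Step 1. Scheduled plug checks, in order**

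| Time | Check | Source |
|---|---|---|
| Visit 2, after insertion | Slit lamp | 7.4.2 item c; key D |
| Visit 3, before surgery | None listed | 7.4.3; schedule tables |
| Visit 3, after surgery | Visual | 7.4.3 item c; key E |
| Visits 4 to 7 | Slit lamp | 7.4.4, 7.4.5; key D |

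The unobserved interval runs from insertion to the end of the operation. It spans both the period governed by 6.1.7.2 and the period governed by 6.1.7.3.

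**Step 2. What else could reveal a loss before surgery**

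- The open question about problems, asked at each visit (7.2.1 item l; 8.1).
- Subject-reported adverse events before surgery (7.4.3 item d).
- The pre-surgery pupil measurement (7.4.3 item a), which brings staff to the eye but is not a plug check.

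The explicit instruction to report a lost plug covers only the time after the operation: "A study subject that has noticed a plug has been extruded or lost during the follow-up period after surgery should immediately contact the Investigator". So the gap is confined to losses that nobody notices.

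**Step 3. Number of eyes**

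The plan has no figure to reproduce here. It names plug loss as a risk (2.3.1) without a rate, and 10.5 says that no formal sample size estimation was done. The arm sizes are consistent: 25 blocks of 3 at 2:1 (10.6.1) give 50 active and 25 placebo.

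Let q be the probability of an unnoticed pre-operative loss. This is an assumption.

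- Expected active eyes affected = 50 × q.
- Probability of at least one = 1 − (1 − q)^50.

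**Step 4. Effect on Day 1 pain**

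For illustration, take the Day 1 pain-free rates that Section 2.1 reports for topical nepafenac 0.1% and vehicle, about 80% and 50%. As a worst case, give every affected active eye the full vehicle rate.

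- Shift per affected eye = (0.80 − 0.50) / 50 = 0.006, or 0.6 percentage points.
- Expected active-arm rate = 0.80 − 0.30 × q.

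**Step 5. Effect on power, same illustration**

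Two-sided 5% normal-approximation test of two proportions, 25 versus 50:

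power = Φ[(d − 1.96 × se0) / se1], where

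- d is the difference in rates;
- se0 = √[p̄(1 − p̄)(1/25 + 1/50)], with p̄ the pooled rate;
- se1 = √[p1(1 − p1)/25 + p2(1 − p2)/50].

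At q = 0: p̄ = (12.5 + 40)/75 = 0.70, se0 = 0.1122, se1 = 0.1149, and power = Φ(0.696) = 75.7%.

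At q = 10%: p̄ = (12.5 + 38.5)/75 = 0.68, se0 = 0.1143, se1 = 0.1164, and power = Φ(0.396) = 65.4%.

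| q (assumed) | Active eyes affected | P(at least one) | Active Day 1 rate | Power |
|---|---|---|---|---|
| 0 | 0 | 0 | 80.0% | 75.7% |
| 2% | 1 | 64% | 79.4% | 73.7% |
| 5% | 2.5 | 92% | 78.5% | 70.7% |
| 10% | 5 | 99.5% | 77.0% | 65.4% |

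These powers only scale the effect. The plan states no power.

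**The case against.** The best reply is that the protocol does not contradict itself. Section 6.1.7.2 works whenever a loss is noticed, and there are several chances to notice one: the question at each visit, adverse event reporting before surgery, and staff looking at an eye whose plug is green with a visible cap (6.1.2, 6.1.6). This stands, and it limits the point to unnoticed losses. None of these routes is a scheduled plug check, however.

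A reader might infer more than the documents support:

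- **That any pre-operative loss is missed and the eye is operated on untreated.** Noticed losses can be acted on. An active eye may have received drug between insertion and loss, and 6.1.7.3 can put a new plug in place after surgery, ahead of the Day 1 assessment. A placebo eye loses no active drug, so for efficacy the relevant denominator is 50, not 75.
- **That each affected subject costs 2 points (1/50) of the active arm's Day 1 rate.** That would require every such subject to change for certain from pain-free to pain. The expected shift in the illustration is 0.6 points.
- **That such subjects would be analysed as normally treated.** The plan does not say so. Section 10.6.3 has each subject and visit assessed for evaluability before the code is broken, and 10.4.2 defines a per-protocol set. Keeping them in an intention-to-treat analysis would be proper in any case.
- **That a migrated plug would go unlooked for.** Section 6.1.7.4 calls for a check of the canaliculi in any subject whose plug has been lost. The text sits under post-operative loss and 6.1.7.3 does not repeat it, but its wording is general.

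The requirement to record a suspected date of loss is a fair point too, but it cannot supply a date that nobody observed.

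**Conclusion.** The point holds for unnoticed losses. After the check at insertion, nothing scheduled confirms that the plug is in place before the operation. An unnoticed pre-operative loss would surface only afterwards, could not be separated from an intra-operative extrusion, and would bypass 6.1.7.2.

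The likely effect on efficacy is modest. Under an assumed 2% to 10% of unnoticed losses, 1 to 5 of 50 active eyes are affected and the expected Day 1 pain-free rate falls by 0.6 to 3 percentage points. That rests on topical-drop rates borrowed for illustration and on the worst-case premise that affected eyes behave fully like vehicle eyes. The true rate of unnoticed loss is not in the documents and could lie below this range.

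For any loss that does go unnoticed, the inability to classify and date it follows whatever the rate. Together with the very low cost of a remedy, this is the main reason to act.

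**What to change.** In Section 7.4.3 and both schedule tables, add a recorded visual inspection of the plug before surgery starts, at the same moment as the existing pre-surgery pupil measurement (key G). Keep the inspection after surgery. Amend key E to cover both, and let the CRF record the result of each.

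The sponsor should reconcile Sections 6.1.7.2, 6.1.7.3 and 7.4.3 so that the extrusion rules match the inspection schedule. Which rule follows from which finding is a clinical decision for the sponsor, and none is proposed here.

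The cost is a few seconds per subject by staff already at the eye, plus one extra CRF field. The downside is an occasional rescheduled operation, which 6.1.7.2 already provides for.

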7.4.4 Visit 4 through Visit 6: Follow-up visits

7.4.4.1 Visit 4: (Day 1 Post-Op)

At this visit the following will be performed on the surgical eye only:

- a. Investigator evaluation of ocular pain
- b. Inspection of the masked punctal plug via the slit lamp
- c. Slit-Lamp examination.
- d. Recording of any reported adverse event(s).
- e. Concomitant medication

Each study subject will be scheduled to return in 2 days for a follow-up study examination (Visit 5, day 3 post-op). The Investigator and/or his/her staff will review with each study subject the proper use or discontinuation of any post-op open-label medications prescribed by the Investigator. Any changes, discontinuation or addition of an open-label medication(s) must be recorded on the Concomitant Medication CRF.

7.4.4.2 Visit 5: (Day 3 \pm 1 Post-Op)

At this visit the following will be performed on the surgical eye only:

- a. Investigator evaluation of ocular pain

NOTE: The Investigator that interviewed and record the subject's response to ocular pain at Visit 4 (Day 1 post-op) should interview the subject at this visit

- b. Monocular Distance Visual Acuity (Uncorrected)
- c. Inspection of the masked punctal plug via the slit lamp
- d. Slit-Lamp examination

NOTE: The Investigator that performed slit-lamp evaluation at Visit 4 (Day 1 post-op) should perform the slit-lamp evaluation at this visit.

- e. Recording of any reported adverse event(s).
- f. Concomitant medication

Each study subject will be scheduled to return in 4 days for a follow-up study examination (Visit 6, day 7 post-op). The Investigator and/or his/her staff will review with each study subject the proper use or discontinuation of any post-op open-label medications prescribed by the Investigator. Any changes, discontinuation or addition of an open-label medication(s) must be recorded on the Concomitant Medication CRF.

7.4.4.3 Visit 6: (Day 7 ± 1 day Post-Op)

At this visit the following will be performed on the surgical eye only:

- a. Investigator evaluation of ocular pain

NOTE: The Investigator that interviewed and record the subject's response to ocular pain at Visit 4 (Day 1 post-op) should interview the subject at this visit

- b. Monocular Distance Visual Acuity (Uncorrected and Best-Corrected)
- c. Manifest Refraction
- d. Inspection of the masked punctal plug via the slit lamp
- e. Slit-Lamp examination

NOTE: The Investigator that performed the slit-lamp evaluation at Visit 4 (Day 1 post-op) should perform the slit-lamp evaluation at this visit.

- f. Recording of any reported adverse event(s).
- g. Concomitant medication

Each study subject will be scheduled to return in 7 days for a follow-up study examination (Visit 7, day 14 post-op). The Investigator and/or his/her staff will review with each study subject the proper use or discontinuation of any post-op open-label medications prescribed by the Investigator. Any changes, discontinuation or addition of an open-label medication(s) must be recorded on the Concomitant Medication CRF.

7.4.5 Visit 7: (Final Study Visit, Day 14 ± 2 days Post-Op)

At the final scheduled study visit the following will be performed on the surgical eye only:

- a. Investigator evaluation of ocular pain

NOTE: The Investigator that interviewed and record the subject's response to ocular pain at Visit 4 (Day 1 post-op) should interview the subject at this visit

- b. Monocular Distance Visual Acuity (Uncorrected and Best-Corrected)
- c. Manifest Refraction
- d. Inspection of the masked punctal plug via the slit lamp
- e. Slit-Lamp examination

NOTE: The Investigator that performed slit-lamp evaluation at Visit 4 (Day 1 post-op) should perform the slit-lamp evaluation at this visit.

- f. Fundus examination
- g. Removal of the masked punctal plug
- h. Recording of any reported adverse event(s).
- i. Concomitant medication

An exit form will be completed at this final study examination (Visit 7), or whenever the study subject completes or leaves the study for any reason. The Investigator and/or his/her staff will review with each study subject the proper use or discontinuation of any post-op open-label medications prescribed by the Investigator. Any changes, discontinuation or addition of an open-label medication(s) must be recorded on the Concomitant Medication CRF.

7.4.6 Early Exit Visit

Any study subject exiting the study early, the Investigator must remove the study subject's masked punctal plug. In addition, the Investigator should record the following:

- a. Investigator evaluation of ocular pain

NOTE: The Investigator that interviewed and record the subject's response to ocular pain at Visit 4 (Day 1 post-op) should interview the subject at this visit

- b. Monocular Distance Visual Acuity (Uncorrected and Best-Corrected)
- c. Manifest Refraction

- d. Inspection of the masked punctal plug via the slit lamp
- e. Slit-Lamp examination

NOTE: The Investigator that performed slit-lamp evaluation at Visit 4 (Day 1 post-op) should perform the slit-lamp evaluation at this visit.

- f. Fundus examination
- g. Removal of the masked punctal plug
- h. Recording of any reported adverse event(s).
- i. Concomitant medication

Any changes, discontinuation or addition of an open-label medication(s) must be recorded on the Concomitant Medication CRF.

